1.2 Schedule of Assessments

Table 1. Schedule of Assessments (SOA)

Day +/- Window	Screen	Baseline	Study Intervention Period	Follow-up Visits		
	-1 or 1	1	Daily until hospital discharge	15 ⁷ ± 2	22 ⁷ ± 3	29 ⁷ ± 3
ELIGIBILITY						
Informed consent	X					
Demographics & Medical History	X					
Review SARS-CoV-2 results	X					
STUDY INTERVENTION						
Randomization		X				
Administration of investigational agent			
 • Remdesivir daily infusion until day 10 or discharge. • Baricitinib or placebo: daily by mouth until day 14 or discharge 			
STUDY PROCEDURES						
Targeted physical exam		X				
Vital signs including SpO ₂ ¹		X ⁴	Daily until discharge ⁸	X ⁹		X ⁹
Clinical data collection ²		X ⁴	Daily until discharge ⁸	X ⁹	X ⁹	X ⁹
Adverse event evaluation		X ⁴	Daily until discharge ⁸	X ⁹	X ⁹	X ⁹
Concomitant medication review		X ⁴	From Day -7 to Day 15			
SAFETY LABORATORY						
Safety hematology, chemistry and liver tests	X ³	X ^{4,5,6,7}	Day 3, 5, 8, 11 (all ± 1 day) if hospitalized ^{6,7}	X ⁹		X ⁹
Pregnancy test for females of childbearing potential	X ³					
RESEARCH LABORATORY						
Blood for plasma to test for PCR SARS-CoV-2		X ^{4,6}	Day 3, 5, 8, 11 (all ± 1 day) if hospitalized			
Oropharyngeal swab ¹⁰		X ^{4,6}	Day 3, 5, 8, 11 (all ± 1 day) if hospitalized	X ⁹		X ⁹
Blood for serum (secondary research)		X ^{4,6}	Day 3, 5, 8, 11 (all ± 1 day) if hospitalized	X ⁹		X ⁹

Notes:

¹Vital signs include temperature, systolic blood pressure, heart rate, respiratory rate, O₂ saturation and level of consciousness. Vital signs collected as part of standard care may be used.

²Refer to Section 8.1.2 of the protocol for details of clinical data to be collected including ordinal score, NEWS, oxygen requirement, mechanical ventilator requirement, etc.

³Screening laboratory tests include: CBC with differential (including absolute neutrophil count and absolute lymphocyte count), ALT, AST, creatinine (and calculate an estimated glomerular filtration rate (eGFR) the formula used is determined

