6.5 Concomitant Therapy

6.5.1 Permitted Concomitant Therapy and Procedures

Receipt of any exclusionary treatments or medications prior to screening will be assessed to determine eligibility as described in the exclusion criteria. This includes use of strong inhibitors of organic anion transporter 3 (OAT3) such as probenecid which are prohibited during the study.

For patients that are eligible for the study, other therapy received prior to enrollment with any other experimental treatment or off-label use of marketed medications that are intended as specific treatment for COVID-19 or the SARS-CoV-2 infection (i.e., post-exposure prophylaxis [PEP]) are permitted but must be discontinued on enrollment. There is no waiting period between discontinuation of these treatments and administration of study products. However, these prior treatments and their end date should be documented on the Concomitant Medication (CCM) form in the Advantage eClinical system.

There are two scenarios in which outpatient experimental treatment or off-label use of marketed medications that are intended as specific treatment for COVID-19 do not need to be discontinued. First, subjects who are taking another antiviral for a concurrent infection (e.g. oseltamivir for an influenza virus, lopinavir/ritonavir for HIV, etc.) or another existing medical condition (e.g. hydroxychloroquine for lupus, etc.) may continue with the treatment. Note that these treatments may be thought of as an off-label medication for COVID-19, however, because they were being used prior to study enrollment for another indication, they are allowable. Second, if there is a written policy or guideline for the local standard of care and treatment of COVID-19 patients or SARS-CoV-2 infection (i.e., not just an individual clinician decision), continuation of these outpatient medications are permitted. This could include lopinavir/ritonavir (Kaletra), hydroxychloroquine or other agents. There should be plans on how the concomitant drugs are stopped in case of additive toxicities.

VTE prophylaxis is recommended for all patients unless there is a major contraindication such as active bleeding events or history of heparin-induced thrombosis.

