9.1.2. Prior and Concomitant Medications

Medication history (concomitant medications) includes a review of all current medications and medications taken within 7 days prior to enrollment through approximately Day 15 or early termination (if Day 15), whichever occurs first.

Summaries of medications that were started prior to dosing and continued at the time of dosing or started after dosing while on study will be presented by WHO Drug Level 1 and 2 Codes, disease severity, and treatment group (Table 53). Summaries of overall use of prohibited medications/therapies listed in Section 6.4 that were started prior to dosing and continued at the time of dosing or started after dosing while on study as well as use by select study days will also be generated (Table 54 and Table 55).

Individual subject listings will be presented for all concomitant medications (Listing 9).

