	Moderate (N=X)		Severe (N=X)		Moderate (N=X)		Severe (N=X)		Moderate (N=X)		Severe (N=X)	
	N	%	n	%	n	%	n	%	n	%	n	%
Any Medication/Therapy	x	xx	x	xx	x	xx	x	xx	x	xx	x	xx
Protease inhibitors	x	xx	x	xx	x	xx	x	xx	x	xx	x	xx
Polymerase inhibitors	x	xx	x	xx	x	xx	x	xx	x	xx	x	xx
Potential Treatments for COVID-19	x	xx	x	xx	x	xx	x	xx	x	xx	x	xx
Chloroquine/Hydroxychloroquine	x	xx	x	xx	x	xx	x	xx	x	xx	x	xx
Other	x	xx	x	xx	x	xx	x	xx	x	xx	x	xx
Corticosteroids	x	xx	x	xx	x	xx	x	xx	x	xx	x	xx
Other anti-inflammatory drugs	x	xx	x	xx	x	xx	x	xx	x	xx	x	xx
Monoclonal Antibodies Targeting Cytokines	x	xx	x	xx	x	xx	x	xx	x	xx	x	xx
Other Biologic Therapies	x	xx	x	xx	x	xx	x	xx	x	xx	x	xx

N = Number of subjects in the As Treated Population.

n=Number of subjects reporting taking at least one medication in the specified category.

Programming Note: only include medications where the end date is missing (i.e. ongoing) or end date is on or after enrollment date

Table 55: Use of Medications of Interest by Study Day, Actual Disease Severity, and Treatment Group – As Treated Population

Study Day	Baricitinib + RDV (N=X)				Placebo + RDV (N=X)				All Subjects (N=X)			
	Moderate (N=X)		Severe (N=X)		Moderate (N=X)		Severe (N=X)		Moderate (N=X)		Severe (N=X)	
	n	%	n	%	n	%	n	%	n	%	n	%
Any Medication of Interest												
Day 1	x	Xx	x	xx	x	xx	x	xx	x	xx	x	xx
Day 3	x	Xx	x	xx	x	xx	x	xx	x	xx	x	xx
Day 5	x	Xx	x	xx	x	xx	x	xx	x	xx	x	xx
Day 8	x	Xx	x	xx	x	xx	x	xx	x	xx	x	xx
Day 11	x	Xx	x	xx	x	xx	x	xx	x	xx	x	xx
...Repeat for all categories and sub-categories of the medications in Section 6.4												
N = Number of subjects in the As Treated Population. n=Number of subjects reporting taking at least one prohibited medication by the specified study day.												

Programming Note: If the start date of the prohibited medication is on or before the specified (actual) study day, then the subject will be denoted as taking the med for that Study Day.

Table 56: Overall Summary of Adverse Events – As Treated Population

Subjects ^a with	Baricitinib + RDV (N=X)						Placebo + RDV (N=X)						All Subjects (N=X)					
	Moderate (N=X)		Severe (N=X)		Any Severity (N=X)		Moderate (N=X)		Severe (N=X)		Any Severity (N=X)		Moderate (N=X)		Severe (N=X)		Any Severity (N=X)	
	N	%	n	%	n	%	n	%	n	%	n	%	n	%	n	%	n	%
At least one adverse event	X	x	x	x	x	x	x	x	x	x	x	x	x	x	x	x	x	X
At least one Severe or Life-threatening (Grade 3 or 4) adverse event	X	x	x	x	x	x	x	x	x	x	x	x	x	x	x	x	x	X

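### Table 55 assigns medication use by day from the start date alone, omits the Table 54 end-date filter, contradicts its own footnote and stops at Day 11

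*SAP*

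**What the plan says.** The Table 55 shell in SAP Appendix 1 has rows for Days 1, 3, 5, 8 and 11 and then the line "Repeat for all categories and sub-categories of the medications in Section 6.4", with no later day. Two statements define what is counted:

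- The programming note sets the test, "If the start date of the prohibited medication is on or before the specified (actual) study day, then the subject will be denoted as taking", and attaches current-use wording to it: "then the subject will be denoted as taking the med for that Study Day".
- The footnote defines the count differently: "n=Number of subjects reporting taking at least one prohibited medication by the specified study day".

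The note for Table 54, the overall summary of the same medications, carries a restriction: "only include medications where the end date is missing (i.e. ongoing) or end date is on or after enrollment date". The Table 53 note has an equivalent one. SAP 9.1.2 introduces Tables 54 and 55 together and describes the drugs as those "started prior to dosing and continued at the time of dosing or started after dosing while on study", adding that use on selected study days will be shown.

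The ACTT-2 schedule of assessments (Protocol Appendix B 1.2) gives the medication review window as "From Day -7 to Day 15"; Appendix B 6.5.2 ends it at discharge if that is sooner. Under Appendix B 6.5.1, earlier treatments aimed at COVID-19 "are permitted but must be discontinued on enrollment", with two listed exceptions, and their end dates are recorded.

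**The concern.** The recording window opens a week before enrollment, and the protocol expects some COVID-19 treatments to have been taken and stopped by the time a subject enters. Records with a start date and an early end date are therefore foreseeable. A rule that looks only at the start date cannot tell such a record from ongoing use: once a drug has started, the subject is counted on every later row, so a category's count cannot fall from Day 1 to Day 11.

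Table 55 is the by-day, by-arm display of corticosteroids, hydroxychloroquine and biologics. A reader would use it to judge whether background treatment differed between arms during follow-up. If some entries are drugs that ended before randomization and others are drugs already stopped, it does not answer that question. If rows stop at Day 11, a drug first started on Days 12 to 15 does not appear at all. SAP 6.4 makes the Day 15 sensitivity analysis depend on use before the Day 15 assessment, so such a drug can alter a subject's value there and still be absent from this table.

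**Working it through.** The plan states no count for this table, so there is no figure to reproduce. The check applies each rule to six hypothetical records, one per subject. The dates are assumed, and enrollment is taken as Day 1.

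Rules for displayed day d:
- Note as written: start ≤ d.
- Start-and-end: start ≤ d, and end missing or ≥ d.
- Table 54 filter: end missing, or on or after Day 1.

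| Record | Note as written | Start-and-end | In Table 54? |
|---|---|---|---|
| A: Day -5 to -1 | 1, 3, 5, 8, 11 | none | No |
| B: Day -3 to 1 | 1, 3, 5, 8, 11 | 1 | Yes |
| C: Day 2 to 4 | 3, 5, 8, 11 | 3 | Yes |
| D: from Day 6, ongoing | 8, 11 | 8, 11 | Yes |
| E: from Day 12, ongoing | none | none | Yes |
| F: Day 13 to 15 | none | none | Yes |

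Three results follow.

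1. *Scope.* Record A is outside SAP 9.1.2 and excluded from Table 54, yet it is on every Table 55 row. With records A to D only, the Day 11 row shows 4 subjects and Table 54 shows 3. In general, let X be the subjects with a drug that ended before enrollment and no drug passing the filter started by Day 11, and let Y be the subjects whose first drug passing the filter started after Day 11. Then Day 11 count minus Table 54 count = X − Y, so Table 55 exceeds Table 54 whenever X > Y. For A to D, X = 1 and Y = 0, and the difference is 4 − 3 = 1.

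2. *Meaning.* Record C is counted on Days 5, 8 and 11 after it ended on Day 4. That is correct for ever-use by day d (the footnote) and incorrect for taking the drug on day d (the note).

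3. *Last row.* Records E and F appear on no current row under either rule. With a Day 15 row both are counted there under either rule. With that row and the Table 54 filter, the cumulative Day 15 count is 5 (B to F), equal to the Table 54 total for these six records. Without the filter it is 6.

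**The case against.** The best defense is the footnote. It describes cumulative use, and for that a start-date rule is right. A reader might infer that Table 55 simply mistakes ever-use for current use; the documents do not support that, because one of the two statements printed with the table is cumulative. What stands is the contradiction between the note and the footnote. The footnote also does not bring drugs that ended before enrollment into scope.

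SAP 9.1.2 can be read as applying one scope to both tables, leaving the note only to assign days. That is a fair account of the intent, but the two preceding tables state the filter explicitly and this one does not, so a programmer following the note would not apply it. SAP 6.4 does mention therapies given before the study, but in setting up the sensitivity analyses, not this table.

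A reader might also infer that a drug stopped on the day of enrollment conflicts with Table 54. It does not: record B passes the Table 54 filter. Only drugs that ended before enrollment create the mismatch.

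On the last row, SAP 9.1.2 promises only selected days, and Days 1, 3, 5, 8 and 11 are ACTT-2's own baseline and in-hospital sampling days. That Day 11 was carried over from the ACTT-1 recording limit is an inference. Late-started drugs are not lost, since Table 54 counts them and Listing 10 gives their start and end days. SAP 17 already allows extra data points. These arguments show that omitting Day 15 is permissible; they do not show that it is useful, given the Day 15 sensitivity analysis.

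**Conclusion.** The point holds as a defect of specification in one descriptive table. As written, the note counts drugs that ended before enrollment on every row, allows Table 55 to exceed Table 54, gives drugs stopped on study a current-use label on all later rows, and disagrees with the footnote. First use on Days 12 to 15 is not shown by day.

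The consequence is small. No test is planned on Table 55, and the medication sensitivity analyses in SAP 6.4 use each subject's own timing of use. A reader might go further and quantify how far balanced pre-enrollment use would dilute a difference between arms. The documents do not support a figure: they give no usage rates, and the shell splits each arm into moderate and severe with no overall per-arm column. The size of the miscount depends on how many subjects have records like A and C, which is unknown at the planning stage.

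The conclusion assumes that the programming note would be applied literally, and the illustration takes enrollment as Day 1.

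**What to change.** Amend the Table 55 specification in three places.

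1. Add the Table 54 filter: include a drug only if its end date is missing or falls on or after enrollment.
2. Choose one definition and use it in the title, note and footnote. For use on day d, require start day ≤ d and end day missing or ≥ d. For cumulative use, keep the start-date test and say cumulative in both the note and the title. The cumulative label is the smaller edit and agrees with the footnote. It also avoids a limit of the data: Protocol Appendix B 6.5.2 has each drug recorded once however often it was given, so a start-to-end span does not prove use on every day within it.
3. Add a Day 15 row for each category and sub-category.

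While editing, replace the remaining references to prohibited medication in the note and footnote with medication of interest, to match the table title.

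The cost is a revised note and footnote, a title change if the table is cumulative, and one extra row per category. End dates are already collected and appear in Listing 10, so no new data are needed and no planned test is affected.

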9.3. Adverse Events

For the calculation of incidence of adverse events (i.e., on a per subject basis), each subject will only be counted once and any repetitions of adverse events within a subject will be ignored; the denominator will be the number of subjects in the Treated population. All adverse events reported will be included in the summaries and analyses.

An overall summary by treatment arm and disease severity of adverse events is presented that includes, but not limited to: subjects with at least one event, at least one related event, at least one SAE, at least one related SAE and at least one AE leading to early termination (Table 56 and Table 57).

Adverse events occurring in 5% of subjects (by MedDRA preferred term) in any treatment group will be presented (Table 58).

The proportion of subjects reporting at least one adverse event will be summarized by MedDRA system organ class and preferred term for each treatment arm, disease severity and overall. Denominators for percentages are the number of subjects in the Treated population.

The following summaries for adverse events will be presented by MedDRA system organ class, preferred term, disease severity and treatment group:

- Treatment-emergent renal adverse events by preferred term (Table 61);
- Treatment-emergent hepatic adverse events by preferred term (Table 62);
- Related adverse events by MedDRA system organ class and preferred term (Table 63);
- Subject listing of non-serious adverse events (Listing 11);
- Bar chart of non-serious related adverse events by severity and MedDRA system organ class (Figure 37);
- Bar chart of non-serious related adverse events by maximum severity and MedDRA system organ class (Figure 40);

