N = Number of Subject in the As Treated Population and specified actual disease severity stratum. n = Number of subjects in a given treatment group who experienced the specified safety event outcome. 95% CI calculated using C-P/Blaker method P-value calculated using Barnard's Exact Test							

Table 73: Analysis of Time to Death, SAEs, or Grade 3 or 4 AEs by Treatment Group – As Treated Population

Actual Disease Severity	Treatment Group	n	Median Time		HR		P-value
			Estimate	95% CI	Estimate	95% CI	
Any Severity (N=X)	Baricitinib + RDV (N=X)	X	x.x	x.x, x.x	x.xx	x.xx, x.xx	x.xxx
	Placebo + RDV (N=X)	X	x.x	x.x, x.x			
Moderate (N=X)	Baricitinib + RDV (N=X)	X	x.x	x.x, x.x	x.xx	x.xx, x.xx	--
	Placebo + RDV (N=X)	X	x.x	x.x, x.x			
Severe (N=X)	Baricitinib + RDV (N=X)	X	x.x	x.x, x.x	x.xx	x.xx, x.xx	--
	Placebo + RDV (N=X)	X	x.x	x.x, x.x			

N= Number of subjects in the As Treated Population and specified actual disease severity stratum.

n = Number of subjects who died or experienced SAEs or Grade 3 or 4 AEs.

HR is the ratio of the hazard of Death/SAE/AE of Grade 3 or 4 in each treatment group estimated from the stratified Cox model. The ratio is Baricitinib + RDV to Placebo + RDV. P-value calculated using the Log-rank test

Table 74: Infections by Treatment Group – As Treated Population, Moderate Disease Severity

Anatomical Location	Pathogen	Baricitinib + RDV (N=X)									Placebo + RDV (N=X)								
		Severe			Life-Threatening			Death			Severe			Life-Threatening			Death		
		n	%	Events	n	%	Events	n	%	Events	n	%	Events	n	%	Events	n	%	Events
Any Location	Any Pathogen	x	x	x	x	x	X	x	x	x	x	x	x	x	x	x	x	x	x
Location 1	Any Pathogen	x	x	x	x	x	X	x	x	x	x	x	x	x	x	x	x	x	x
	Pathogen 1	x	x	x	x	x	X	x	x	x	x	x	x	x	x	x	x	x	x
	Pathogen 2	x	x	x	x	x	X	x	x	x	x	x	x	x	x	x	x	x	x
Location 2	Any Pathogen	x	x	x	x	x	X	x	x	x	x	x	x	x	x	x	x	x	x
	Pathogen 1	x	x	x	x	x	X	x	x	x	x	x	x	x	x	x	x	x	x
	Pathogen 2	x	x	x	x	x	X	x	x	x	x	x	x	x	x	x	x	x	x

Note: Percents may not add to 100 because participants may have infections with multiple pathogens. All Grade 3 or 4 infections are also reported as AEs.
 N=Number of participants randomized to Treatment group.
 n=Number of participants with infection.

Tables with similar format:

Table 75: Opportunistic Infections by Treatment Group – As Treated Population, Moderate Disease Severity

Table 76: Infections by Treatment Group – As Treated Population, Severe Disease Severity

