Table 77: Opportunistic Infections by Treatment Group – As Treated Population, Severe Disease Severity

Table 78: Infections by Treatment Group – As Treated Population, All Subjects

Table 79: Opportunistic Infections by Treatment Group – As Treated Population, All Subjects

Programming Notes for Table 75, Table 77, Table 79: Opportunistic infections will be identified by the sponsor and will be documented in a spreadsheet/SAS dataset to be imported into ADaM dataset programming.

Table 80: Abnormal Laboratory Results of Grade 3 or 4 by Parameter, Maximum Severity, Time Point, and Treatment Group – As Treated Population

Laboratory Parameter	Time Point	Treatment Group	N	Severe/ Grade 3		Life Threatening/ Grade 4		Severe/Grade 3 or Life Threatening/Grade 4	
				n	%	n	%	n	%
Any Parameter	Baseline	Baricitinib + RDV	x	x	x	x	x	x	x
		Placebo + RDV	x	x	X	x	x	x	x
	Day 3	Baricitinib + RDV	x	x	X	x	x	x	x
		Placebo + RDV	x	x	X	x	x	x	x
	Day 5	Baricitinib + RDV	x	x	X	x	x	x	x
		Placebo + RDV	x	x	X	x	x	x	x
	Day 8	Baricitinib + RDV	x	x	X	x	x	x	x
		Placebo + RDV	x	x	X	x	x	x	x
	Day 11	Baricitinib + RDV	x	x	X	x	x	x	x
		Placebo + RDV	x	x	X	x	x	x	x
	Day 15	Baricitinib + RDV	x	x	X	x	x	x	x
		Placebo + RDV	x	x	X	x	x	x	x
	Day 29	Baricitinib + RDV	x	x	X	x	x	x	x
		Placebo + RDV	x	x	X	x	x	x	x
	Maximum Severity Post Baseline	Baricitinib + RDV	x	x	X	x	x	x	x
		Placebo + RDV	x	x	X	x	x	x	x

Each parameter will be summarized individually similar to the above...

The “Max Post Baseline” rows indicate the maximum severity experienced by each subject at any time point post baseline, including unscheduled assessments and assessments beyond Day 29.
N = Number of subjects in the As Treated Population

Programming Note: D-dimer and CRP results are not included in this table. Include all lab parameters that are being graded in this table.

Tables with similar format:

Table 81: Abnormal Laboratory Results of Grade 3 or 4 by Parameter, Maximum Severity, Time Point, and Treatment Group – Moderate Disease Severity, As Treated Population

Table 82: Abnormal Laboratory Results of Grade 3 or 4 by Parameter, Maximum Severity, Time Point, and Treatment Group – Severe Disease Severity, As Treated Population

Programming Notes for Table 81 and Table 82: Actual Disease Severity will be used. Include all lab parameters that are being graded in this table.

Table 83: Treatment-Emergent Laboratory Abnormalities - As Treated Population

Laboratory Parameter	Grade	Baricitinib + RDV (N=X)			Placebo + RDV (N=X)		

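### The footnote shared by the infection tables (SAP Tables 74-79) defines N by randomized arm, in conflict with their As Treated titles and the SAP's own safety rules; read literally, it would also shrink the severity-specific percentages.

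*SAP*

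**What the plan says.** SAP Appendix 1 gives one full shell for infections, "Table 74: Infections by Treatment Group – As Treated Population, Moderate Disease Severity". Tables 75-79 are listed beneath it as having a similar format. They include "Table 76: Infections by Treatment Group – As Treated Population, Severe Disease Severity", "Table 77: Opportunistic Infections by Treatment Group – As Treated Population, Severe Disease Severity" and "Table 78: Infections by Treatment Group – As Treated Population, All Subjects", so Tables 74-77 are severity-specific and Tables 78-79 are not.

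The Table 74 footnote defines the denominator as "N=Number of participants randomized to Treatment group" and the numerator as "n=Number of participants with infection". The one programming note, for Tables 75, 77 and 79, covers how opportunistic infections are identified and leaves N alone.

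Elsewhere the SAP sets a different rule:

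- Section 6.3.1 limits the As Treated population to randomized subjects who took at least one tablet, and classifies As Treated safety outcomes by actual treatment and actual severity stratum.
- Section 9.3 says of adverse event incidence that "the denominator will be the number of subjects in the Treated population". Section 15 records that this population was renamed As Treated.
- Section 9.4 takes the infection summary from the adverse event CRF, so these are adverse event data.
- Table 73, immediately before, has "N= Number of subjects in the As Treated Population and specified actual disease severity stratum", and Table 72 uses near-identical wording.

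**The concern.** The title and the footnote of the same table name different populations. A title restricted to treated subjects in one stratum fixes the numerator; the footnote then offers a denominator with neither restriction, counted by assigned rather than received treatment.

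Serious infection is a boxed-warning risk of baricitinib (Protocol Appendix B, Section 2.2.3.1), and a dedicated follow-up form is completed for each reported infection (Appendix B, Section 8.3.5.1). Tables 74-79 report those data by site, pathogen and grade. A reader using the Severe table wants the infection risk among severe patients. If N were the whole arm, the table would not give that risk, and its percentages could not be set beside those of the Moderate table.

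**Working it through.** **The plan's own figure.** The documents state no infection rate or infection denominator. The relevant planned number is the arm size (SAP Section 5). The events formula with a rate ratio of 1.25, two-sided 0.05 and 85% power gives 4 × (1.96 + 1.036)² / (ln 1.25)² = 721.3, against 723 stated. Then 723 / 0.70 = 1032.9, against 1032 stated. At 1:1 allocation that is 1032 / 2 = 516 per arm. The plan's figure reproduces.

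**Step 1: population and classification.** This step needs no assumption.

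| Source | Population | Treatment | Stratum |
|---|---|---|---|
| Titles, Tables 74-77 | As Treated | not stated | one stratum |
| Titles, Tables 78-79 | As Treated | not stated | all subjects |
| SAP 6.3.1, safety | As Treated | actual | actual |
| SAP 9.3 | Treated | not stated | not stated |
| Footnotes, Tables 72-73 | As Treated | not stated | actual |
| Footnote, Tables 74-79 | Randomized | randomized arm | not stated |

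The last row disagrees with the others on population, and with Section 6.3.1 on treatment classification. It is silent on stratum.

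**Step 2: effect of a literal reading.** Let p be the true infection proportion among As Treated subjects in a stratum, s the stratum's share of the arm and t the treated fraction. The stratum count is p × s × t × 516. Divided by 516, the printed percentage is p × s × t.

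Neither s, t nor p is in the documents. Assume p = 15% against 10%, and t = 1:

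| s | Printed percentages | Gap a reader would see (true gap 5.0 points) |
|---|---|---|
| 0.2 | 3.0% v 2.0% | 1.0 |
| 0.3 | 4.5% v 3.0% | 1.5 |
| 0.5 | 7.5% v 5.0% | 2.5 |
| 0.8 | 12.0% v 8.0% | 4.0 |

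For s = 0.3 in full: the stratum holds 0.3 × 516 = 154.8 per arm; 15% of that is 23.2, and 23.2 / 516 = 4.5%.

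If the severe share is 20% to 50%, the moderate share is 50% to 80%. The factor is then 0.2 to 0.5 in the Severe tables and 0.5 to 0.8 in the Moderate tables. A treated fraction of 95% lowers each figure by a further 5%.

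**Step 3: the ratio.** The printed ratio is (p₁ s₁ t₁) / (p₂ s₂ t₂). With equal s × t in both arms it stays at 15 / 10 = 1.5. Randomization is stratified by severity (SAP 4.2.3), so large imbalance is unlikely. With shares of 0.30 and 0.32 the printed values would be 4.5% and 3.2%, a ratio of 1.41.

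**Step 4: Tables 78-79.** Here s = 1, so apart from any subject given the wrong treatment only t matters. With t between 0.95 and 1, a true 10% prints as 9.5% to 10%.

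**The case against.** The strongest reply is that the whole-arm denominator is only the literal reading, and not the most natural one. The SAP often leaves the stratum out of an N footnote when a title or column header supplies it. Table 53 has separate Moderate and Severe columns, each with its own N, under a footnote that mentions only the As Treated population. Tables 59-60, 81-82 and 85-86 inherit N footnotes that name no stratum. Tables 72-73 hold several strata in one table and so have to name them; Tables 74-77 carry theirs in the title. A programmer guided by the title and Section 6.3.1 would use the stratum count, and the footnote never says that the percentage is n/N. This stands.

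A reader might therefore infer that the planned tables will understate infection risk in severe patients two- to five-fold (1 / 0.5 to 1 / 0.2) and shrink the arm difference to match. The documents do not support that as a fact. It needs the literal reading and an assumed severe share of 20% to 50%. The tables show counts, percentages and events, with no arm difference, interval or test, and Table 56 gives As Treated Ns by actual stratum from which percentages could be recomputed.

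The reply does not rescue the word randomized. The comparable footnotes to Tables 53, 58, 80 and 84 omit the stratum but do name the As Treated population; the Table 74 footnote does not. Nor does convention settle actual against randomized severity for Tables 74-77: Tables 59-60, 81-82 and 85-86 each carry a note specifying actual severity, and Tables 74-77 carry none.

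**Conclusion.** The point holds as an internal inconsistency of minor severity. The footnote to Tables 74-79 names the wrong population and the wrong treatment classification against the tables' titles, SAP 6.3.1, SAP 9.3 and Tables 72-73, and nothing in the shells corrects it. Even a correctly computed table would publish a false definition of N for a boxed-warning harm.

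The dilution in Tables 74-77 is conditional. It arises only if the footnote is followed over the title, and its factor is the stratum share times the treated fraction, neither of which the documents give. The direction would be certain, because a stratum is a subset of the arm; the size is not. The absolute gap that a reader takes from the table would shrink, while the risk ratio would be roughly preserved. Tables 78-79 are exposed only to undosed or wrongly treated subjects. No primary, key secondary or formally tested safety analysis is affected.

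**What to change.** Replace the N footnote:

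- Tables 74-77: N is the number of As Treated subjects, counted by actual treatment, in the actual disease severity stratum that the table covers.
- Tables 78-79: N is the number of As Treated subjects, counted by actual treatment.
- All six tables: state that the percentage is n/N.

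This brings the shells into line with rules the SAP already contains. The cost is one footnote edit in two variants; no new data are needed, and no programming beyond confirming the denominator.
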